8.3. Clinical Laboratory Tests

8.3.1. Laboratory Value Definitions

Laboratory values and change from baseline values will be summarized descriptively by visit for numeric laboratory parameters. Baseline will be determined according to Section 4.1.3. If there are multiple values that meet the criteria for baseline, additional rules may be provided after consultation with the medical monitor to delineate which value will be defined as baseline.

Laboratory test values will be assessed for severity based on the numerical component of CTCAE v5.0.

8.3.2. Laboratory Value Summaries

All test results and associated normal ranges from central laboratories will be reported in SI units. All tests with numeric values will have a unique unit. Any laboratory test results and associated normal ranges from local laboratories will be converted to SI units.

Numeric laboratory values, baseline values, postbaseline values, change from baseline, and percentage change from baseline will be summarized descriptively by visit. The number and percentage of participants with the laboratory values being low, normal, and high will be summarized by visit. In addition, mean change from baseline will be plotted over time for selected laboratory parameters, including phosphate.

Severity grades will be assigned to laboratory test values based on the numerical component of CTCAE v5.0. Shift tables will be presented showing change in CTCAE grade from baseline to worst grade postbaseline. Separate summaries for abnormally high and abnormally low laboratory values will be provided when the laboratory parameter has both high and low grading criteria. The denominator for the percentage calculation will be the number of participants in the baseline category. The number of participants who experienced worsening of laboratory abnormalities will be summarized by maximum severity.

8.3.3. Potential Drug-Induced Liver Injuries

Participants with elevated alanine aminotransferase or aspartate aminotransferase $\geq 3 \times \text{ULN}$ range and alkaline phosphatase $< 2 \times \text{ULN}$ range accompanied by total bilirubin $\geq 2 \times \text{ULN}$ range at the same visit will be listed by cohort.

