| b | Hemoglobin | $\leq 9 \text{ g/dL}$ (transfusion allowed with a 2-week washout period) |
| c | ANC | $\leq 1.5 \times 10^9/\text{L}$ |
| Hepatic | | |
| d | ALT | $\geq 3 \times \text{ULN}$ ($> 5 \times \text{ULN}$ for liver metastasis) |
| e | AST | $\geq 3 \times \text{ULN}$ ($> 5 \times \text{ULN}$ for liver metastasis) |
| f | Total bilirubin | $\geq 1.5 \times \text{ULN}$ ($\geq 2.5 \times \text{ULN}$ if Gilbert's syndrome or liver metastasis) |
| g | Alkaline phosphatase | $\geq 3 \times \text{ULN}$ |
| Renal | | |
| h | Serum creatinine clearance | $\leq 30 \text{ mL/minute}$ based on Cockcroft-Gault formula |
| Chemistry | | |
| i | Serum phosphate | $> \text{ULN}$ |
| j | Serum calcium | Outside of normal range or serum albumin-corrected calcium outside of the normal range when serum albumin is outside of the normal range |

12. History of calcium and phosphate homeostasis disorder or systemic mineral imbalance with ectopic calcification of soft tissues (exception: commonly observed calcifications in soft tissues such as the skin, kidney tendon, or vessels due to injury, disease, or aging in the absence of systemic mineral imbalance).
13. Significant gastrointestinal disorder(s) that could interfere with absorption, metabolism, or excretion of study drug.
14. Clinically significant or uncontrolled cardiac disease including unstable angina, acute myocardial infarction within 6 months before Day 1 of study drug administration, New York Heart Association Class III or IV congestive heart failure, and uncontrolled arrhythmia (participants with pacemaker or with atrial fibrillation and well controlled heart rate are allowed).
15. History or presence of an abnormal ECG that, in the investigator's opinion, is clinically meaningful. A screening QTcF interval > 480 milliseconds is excluded. For participants with an intraventricular conduction delay (QRS interval > 120 ms), the JTc interval may be used in place of the QTc with medical monitor approval. The JTc must be ≤ 340 milliseconds if JTc is used in place of the QTc.
16. Active chronic or current infectious disease requiring systemic antibiotic, antifungal, or antiviral treatment within 2 weeks before enrollment (participants with asymptomatic chronic infections on prophylactic treatment are allowed).

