| Blood Chemistries | Hematology | Urinalysis With Microscopic Examination | Serology | Coagulation |
|--|---|---|--|-------------|
| Albumin | Complete blood count, including: | Color and appearance | HBsAg | PT |
| Alkaline phosphatase | 
 • Hemoglobin • Hematocrit • Platelet count • Red blood cell count • WBC count | pH and specific gravity | HBsAg antibody | PTT or aPTT |
| ALT | | Bilirubin | Hepatitis B core antibody | INR |
| AST | | Glucose | HCV antibody | |
| Amylase | | Ketones | NOTE: If any of the above are positive, HBV-DNA, HCV-RNA may be done to assess risk of reactivation, if indicated (eg, no history of immunization) | |
| Bicarbonate or CO ₂ (not applicable in Japan) | | Leukocytes | | |
| Blood urea nitrogen or urea | | Nitrite | | |
| Calcium | | Occult blood | | |
| Chloride | | Protein | | |
| Creatinine | | | | |
| Glucose | | | | |
| Lactate dehydrogenase | | | | |
| Lipase | | | | |
| Magnesium | | | | |
| Phosphate | | | | |
| Potassium | | | | |
| Sodium | | | | |
| Total bilirubin | | | | |
| Direct bilirubin (if total bilirubin is elevated above ULN) | Absolute values must be provided for: | | | |
| Total protein | 
 • WBC differential laboratory results | | | |
| Uric acid | | | | |
| Vitamin D (25-hydroxyvitamin D and 1,25-dihydroxyvitamin D) ^a | | | | |

Note: Additional tests may be required, as agreed upon by the investigator and sponsor, based on emerging safety data or to rule out a diagnosis.

^a Results not required prior to dose administration.

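### A participant admitted with ALP of 2 to < 3 × ULN cannot appear in the potential liver-injury listing while ALP stays at or above 2 × ULN

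*SAP*

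**What the plan says.** SAP 8.3.3 sets three conditions that must hold together:

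- Transaminases: "Participants with elevated alanine aminotransferase or aspartate aminotransferase $\geq 3 \times \text{ULN}$ range".
- ALP: "alkaline phosphatase $< 2 \times \text{ULN}$ range accompanied by total bilirubin".
- Bilirubin: "total bilirubin $\geq 2 \times \text{ULN}$ range at the same visit will be listed by cohort".

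Each is a fixed multiple of ULN. The section has no baseline term and no restriction to postbaseline visits. The output is Listing 2.8.8 in SAP Appendix A.

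Protocol 5.2, Table 7, sets the screening limits for the same tests:

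- The ALT row reads "ALT | $\geq 3 \times \text{ULN}$ ($> 5 \times \text{ULN}$ for liver metastasis"; the AST row has the same limits.
- Total bilirubin excludes from 1.5 × ULN, relaxed to 2.5 × ULN "if Gilbert's syndrome or liver metastasis".
- ALP has a single limit with no exceptions: "Alkaline phosphatase | $\geq 3 \times \text{ULN".

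**The concern.** An ALP condition in a liver-injury rule serves to separate a hepatocellular pattern from a cholestatic one. It cannot do that when the raised ALP was there before the first dose: the participant is screened out because of an old abnormality, not because of what happened on drug.

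At stake is case-finding in a single-arm study with no data monitoring committee. SAP Appendix A plans no table or plot of transaminases against bilirubin. The shift tables take one laboratory parameter at a time, and the clinically notable adverse event groupings in SAP Table 5 have no hepatic category. Listing 2.8.8 is thus the only place where the combination is assembled, and its rule does not fit the population that Table 7 admits.

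**Working it through.** The plan states no figure on this point, so there is none to reproduce. The check compares two sets of thresholds, all in multiples of ULN. Let T be the higher of ALT and AST, P be ALP and B be total bilirubin.

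**Inputs**

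- Listing rule (SAP 8.3.3), same visit: T ≥ 3 and P < 2 and B ≥ 2.
- Eligibility at screening (Protocol Table 7), no exception: T < 3, P < 3, B < 1.5.
- Gilbert's syndrome: as above, but B < 2.5.
- Liver metastasis: T ≤ 5, P < 3, B < 2.5.

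**1. The ALP gap.** Eligibility allows P < 3 and the listing needs P < 2, so the admitted but unlistable band is 2 ≤ P < 3. With P held in that band the rule fails whatever T and B are:

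| ALP | ALT | Bilirubin | Listed? |
|---|---|---|---|
| 1.99 | 10 | 5 | yes |
| 2.0 | 10 | 5 | no |
| 2.5 | 10 | 5 | no |
| 2.99 | 10 | 5 | no |

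Trying ALP of 2, 2.25, 2.5 and 2.99 with ALT up to 50 and bilirubin up to 30 gives no listed combination.

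**2. Gilbert's syndrome.** Entry bilirubin of 2 ≤ B < 2.5 is allowed and already meets the bilirubin condition. With B = 2.2 unchanged and P < 2, ALT of 2.9 is not listed and ALT of 3.0 is. A participant with no exception enters with B < 1.5, so bilirubin must rise to at least 2 before listing is possible.

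**3. Entry values.** Without liver metastasis, T < 3 at screening, so the qualifying screening values cannot satisfy the rule. With liver metastasis, T of 3 to 5, B of 2 to < 2.5 and P < 2 are admissible together. All three conditions could then be met before the first dose, and SAP 8.3.3 does not exclude pre-dose values.

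**4. Size.** The documents give no distribution of entry ALP. Purely as an assumption, let 1% to 5% of about 164 participants enter in the band: 0.01 × 164 = 1.6 to 0.05 × 164 = 8.2 people. These are people with raised ALP, not missed cases. A missed case also needs T ≥ 3 and B ≥ 2 on study. If 1% to 5% of them did so (also an assumption), the expected number missed is 0.01 × 1.64 = 0.016 to 0.05 × 8.2 = 0.41.

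**The case against.** The strongest reply is that nothing serious would go unseen, and most of it stands.

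- **Other outputs.** ALT or AST above 5 × ULN falls under the interruption guidance in Protocol Table 9. Protocol 9.1 makes a laboratory result that requires a change in study drug a reportable adverse event. Such a case should appear in Table 3.2.19 and Listing 2.7.6. The values also appear in Listing 2.8.2 and, where abnormal, Listing 2.8.6, and they feed Tables 3.3.3.2 and 3.3.3.5. For ALT or AST between 3 and 5 × ULN the adverse event route is less certain, because that row of Table 9 does not apply. The chemistry outputs still hold the values, but do not pair them.
- **Not permanent.** A reader might infer that these participants can never be listed. That goes too far: chemistry is repeated through treatment, and any visit with ALP below 2 × ULN makes listing possible at that visit.
- **No stated inference.** A reader might also infer that an empty Listing 2.8.8 is meant to show that there were no potential cases. Neither document says so. SAP 8.3.3 only requires a listing, and SAP 3.2 calls all analyses exploratory.
- **Gilbert's syndrome.** Treating this as an error of equal weight is not supported. It puts an extra person into a listing of potential cases, and the change proposed here would still list that person, with baseline values beside the result.
- **Unseen layouts.** Sample displays are in a separate document, so Listing 2.8.8 may already carry ALP or baseline columns. Columns cannot help a participant whom the rule keeps out.

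The reply that filter versus flag is only a matter of display does not stand. A filter removes the participant from the listing; a flag keeps the same information about pattern and removes no one.

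**Conclusion.** The mismatch is real and follows from the thresholds alone. While ALP remains at 2 × ULN or above, a participant validly admitted with ALP of 2 to < 3 × ULN is outside Listing 2.8.8 whatever ALT, AST and bilirubin do. The Gilbert's effect is secondary. It is over-inclusion, and it needs unchanged bilirubin and ALP below 2 × ULN.

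The severity is minor. No endpoint, estimate or stopping decision depends on this listing, and the underlying values are reported elsewhere. The number affected is not in the documents. Under the assumed rates shown above, the expected number of missed cases is below one. The documents do not support a claim that 2 to 8 cases would be missed, because that count is of people with an assumed raised entry ALP.

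**What to change.** In SAP 8.3.3, list every participant with postbaseline ALT or AST ≥ 3 × ULN and total bilirubin ≥ 2 × ULN at the same visit, regardless of ALP. In Listing 2.8.8, show ALP with a flag for < 2 or ≥ 2 × ULN, and show baseline ALT, AST, ALP and total bilirubin so that pre-existing elevations can be recognised.

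The cost is one reworded sentence and a few columns. All four tests are already in Protocol Table 12, and baseline is defined in SAP 4.1.3, so no new data are needed and no clinical rule changes. Appendix A lets the output lists change without a SAP amendment where the nature of the analysis is unaffected, but the listing criterion is stated in the body of the SAP and should be changed there. The downside is that a few cholestatic cases will enter the listing; the ALP flag identifies them.

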| Visit Day (Range) | Screening Days -28 to -1 | Treatment | | | | EOT | Follow-Up | | | Notes | | |
|------------------------------|--------------------------------|-----------|------------|-----------|------------|-----|----------------------------|---|---|---|--|--|
| | | Cycle 1 | | Cycles 2+ | | | Safety EOT + 30 Days | Disease Every 9 Weeks ± 7 Days | Survival Every 8 Weeks (± 14 Days) | | | |
| | | Day 1 | (± 3 Days) | Day 15 | (± 3 Days) | | | | | | | |
| Efficacy assessments | | | | | | | | | | | | |
| Brain MRI | X | | | | X* | X† | | X | | *Once every 3 cycles starting at the end of Cycle 3 (± 7 days). †Perform at EOT if not done within 1 month prior to EOT. | | |
| Karnofsky performance status | X | X | | | X | X | X | X | | | | |
| Survival | | | | | | | | | X | | | |

Table 4: Schedule of Laboratory Assessments

| Procedure | Screening | Treatment | | | EOT | Follow-Up | Notes |
|--|-------------------|-----------|---------------------|----------------------|---------------------|---------------|---|
| | Days -28 to -1 | Cycle 1 | | Cycles 2+ | | Safety | |
| | | Day 1 | Day 8 (± 3 Days) | Day 15 (± 3 Days) | Day 1 (± 3 Days) | EOT + 30 Days | |
| Clinical laboratory assessments | | | | | | | |
| Blood chemistries | X | X* | X | X | X† | X | X |
| | | | | | | | *If screening is performed within 14 days of Cycle 1 Day 1, additional sample not required. †HP in Cycle 1 requires Day 8 testing of serum phosphate in Cycles 2+ until phosphate is < 7 mg/dL on Day 8 for at least 2 consecutive cycles on stable dose of binders. |
| Hematology | X | X* | | | X | X | |
| | | | | | | | *If screening is performed within 14 days of Cycle 1 Day 1, additional sample not required. |
| Coagulation panel | X | X* | | | X | X | |
| | | | | | | | *If screening is performed within 14 days of Cycle 1 Day 1, additional sample not required. |
| Endocrine function (PTH only) | X | | | | X* | X | |
| | | | | | | | *Every 3 cycles on Day 1 starting with Cycle 3. |
| Serology | X | | | | | | |
| IDH mutation status | X | | | | | | Only if not available prior to screening. |
| MGMT promoter methylation status | X | | | | | | Only if not available prior to screening. |
| 1p/19q codeletion | X | | | | | | To be assessed in participants with oligodendrogiomas only if not available prior to screening. |
| Urinalysis | X | | | | | | |
| Pregnancy testing | X | X | | | X | X | X |
| | | | | | | | Serum at screening, EOT, and safety follow-up, urine at other timepoints. |

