8.3.7. Laboratory Assessments

See [Table 12](#) for the list of clinical laboratory tests to be performed and [Table 4](#) for the timing and frequency. A certified laboratory local to the investigative site will perform all clinical laboratory assessments for safety (ie, blood chemistries, hematology assessments, coagulation tests, endocrine function, and urinalysis). The investigative site will enter the laboratory results and laboratory normal ranges into the eCRF. Additional testing may be required by the sponsor based on emerging safety data. Additional tests may also be performed if clinically indicated.

A central laboratory will analyze all PK and translational samples. Information regarding collection, processing, and shipping of laboratory assessments is provided in the Laboratory Manual.

Serum phosphate testing is required on Day 8 in Cycles 2+ if a participant develops HP during Cycle 1. Parathyroid hormone (endocrine) testing is required at baseline and Day 1 of every third cycle (starting with Cycle 3) as parathyroid hormone plays a role in calcium and phosphate hemostasis ([Khundmiri et al 2016](#)).

Clinically significant abnormal laboratory findings are those that are not associated with the underlying disease, unless judged by the investigator to be more severe than expected for the participant's condition. All laboratory tests with values considered clinically significantly abnormal during participation in the study or within 30 days after the last dose of study treatment should be repeated until the values return to normal or baseline or are no longer considered clinically significant by the investigator or medical monitor.

Screening laboratory assessments for hematology, chemistry, and coagulation must be performed within 14 days before Cycle 1 Day 1. If performed more than 14 days before Cycle 1 Day 1, then the tests must be repeated and eligibility confirmed before study treatment administration on Cycle 1 Day 1.

Laboratory sample collection on Cycle 1 Day 1 must be performed before study treatment administration. After Cycle 1, predose laboratory procedures can be conducted up to 72 hours before study treatment administration (within the 3-day study window), and results should be reviewed by the investigator or qualified designee and found to be acceptable before a new cycle of treatment is initiated.

Table 12: Required Laboratory Analytes

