4.1.5. Cycle Length and Duration

Cycle 1 Day 1 is the day that the first dose of pemigatinib is administered. The scheduled cycle length is 21 days. The actual Day 1 of subsequent cycles will correspond with the first day of administration of pemigatinib in that cycle. The date of the Day 1 of subsequent cycles recorded on the eCRF will be used as the Day 1 of the subsequent cycles.

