4.1.6. Analysis Window

For parameters that will be summarized by visit, the nominal visit, as recorded on the eCRF, will be used. There will be no additional analysis windowing done based on the assessment date.

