2.6.2	Best Overall Response, Duration of Response, Progression-Free Survival, and Overall Survival
2.6.3	Overall Response Assessment by Visit
2.6.4	Response Assessment: Measurable Disease
2.6.5	Response Assessment: Nonmeasurable Disease
2.6.6	Response Assessment: New Lesions
2.6.8	FGFR Alterations

Listing No.	Title
2.6.9	NANO Scale
2.6.10	Karnofsky Performance Status Scores
2.6.13	Corticosteroid Intake
2.7.1	Adverse Events
2.7.2	Serious Adverse Events
2.7.3	Grade 3 and Higher Adverse Events
2.7.4	Fatal Adverse Events
2.7.5	Treatment-Related Adverse Events
2.7.6	Adverse Events Leading to Interruption, Reduction, or Discontinuation of Pemigatinib
2.7.7	Sponsor-Defined Clinically Notable Adverse Events
2.8.1	Clinical Laboratory Values – Hematology
2.8.2	Clinical Laboratory Values – Chemistry
2.8.3	Clinical Laboratory Values – Coagulation
2.8.4	Clinical Laboratory Values – Endocrine
2.8.5	Abnormal Clinical Laboratory Values – Hematology
2.8.6	Abnormal Clinical Laboratory Values – Chemistry
2.8.7	Abnormal Clinical Laboratory Values – Coagulation
2.8.8	Potential Drug-Induced Liver Injuries
2.9.1	Vital Signs
2.9.2	Abnormal Vital Sign Values
2.9.3	Alert Vital Sign Values
2.10.1	12-Lead ECG Values
2.10.2	Abnormal 12-Lead ECG Values
2.10.3	Alert 12-Lead ECG Values
2.11.1	Eye Examinations

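### SAP 8.3.3 does not flag a potential liver injury when the transaminase and bilirubin thresholds are crossed only at different visits

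*SAP*

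**What the plan says.** SAP 8.3.3 sets three laboratory limits: ALT or AST at least 3 × ULN, ALP below 2 × ULN, and total bilirubin at least 2 × ULN. Participants meeting them "at the same visit will be listed by cohort". The output is Listing 2.8.8 in SAP Appendix A, titled "Potential Drug-Induced Liver Injuries". Appendix A has no matching table or figure.

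SAP 4.1.6 uses the nominal eCRF visit for results summarized by visit and adds: "There will be no additional analysis windowing done based on the assessment date".

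Protocol Table 4 schedules blood chemistry at screening, on Cycle 1 Days 1, 8 and 15, on Day 1 of each later cycle, at end of treatment and at safety follow-up. SAP 4.1.5 states: "The scheduled cycle length is 21 days". Under Protocol 8.3.7, tests with clinically significant abnormal values "should be repeated until the values return to normal or baseline", or until they are no longer judged clinically significant. Protocol 8.6 allows unscheduled visits and has them recorded as such in the eCRF.

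**The concern.** A listing of this kind is a screen. Its job is to bring forward every participant who deserves individual review, so it should lean towards sensitivity. Transaminase and bilirubin need not be above their limits on the same day. Transaminase may already be falling when bilirubin crosses, particularly as Protocol Table 9 interrupts study drug when AST or ALT exceeds 5 × ULN. If the bilirubin elevation is found at a later scheduled draw, or at a repeat recorded as an unscheduled visit, it belongs to a different visit from the transaminase elevation and the two are not paired.

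At stake is how an empty or short Listing 2.8.8 is read. No other planned output links the two analytes. The clinically notable adverse event groups in SAP Table 5 contain no hepatic category, and Protocol 9.5 (Events of Clinical Interest) is marked not applicable.

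**Working it through.** The plan gives no figure to reproduce. The check applies the rule to simple patterns and then looks for another output that would catch what it leaves out.

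**Step 1. The rule.** However the sentence in SAP 8.3.3 is parsed, the transaminase and bilirubin limits must both be met at one visit. Neither document gives a rule for elevations at different visits.

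**Step 2. Spacing of scheduled draws.**
- Cycle 1: 8 − 1 = 7 days and 15 − 8 = 7 days. From Day 15 to Cycle 2 Day 1 (study day 22): 22 − 15 = 7 days.
- From Cycle 2: 21 days between successive Day 1 draws.
- With the ± 3-day visit window at both ends, the longest such gap is 21 + 3 + 3 = 27 days.

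**Step 3. Hypothetical patterns.** Values are assumptions, in multiples of ULN, with ALP at 1.2 throughout. Pattern (c) is pattern (a) with the visits reversed.

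| Pattern | Visit 1 ALT / bilirubin | Visit 2 ALT / bilirubin | Both limits at one visit? | Listed under SAP 8.3.3? |
|---|---|---|---|---|
| (a) | 6 / 1.2 | 2.5 / 2.4 | No | No |
| (b) | 8 / 1.5 | 4 / 2.5 | Yes, visit 2 | Yes |
| (c) | 2.5 / 2.4 | 6 / 1.2 | No | No |

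Patterns (a) and (c) cross both limits and are not listed. In (b) the peaks fall at different visits, yet the participant is listed because ALT is still above 3 × ULN when bilirubin crosses. What matters is whether the threshold elevations ever coincide, not when each analyte peaks. Pattern (c) shows that a remedy looking only forward from the transaminase elevation would leave the same kind of gap.

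**Step 4. The ALP condition.** Protocol Table 7 excludes ALP at entry only from 3 × ULN upward. A participant can therefore enrol with ALP at or above 2 and below 3 × ULN, and cannot be listed while it stays there.

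**Step 5. Other outputs.** Listings 2.8.2 and 2.8.6 show chemistry values and abnormal chemistry values. The shift and worsening tables (SAP 8.3.2) take the worst postbaseline grade for each parameter. All of these work on one analyte at a time, so none identifies the combination.

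**The case against.** The case for leaving the rule alone has several parts.

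- **The rule is explicit and contradicts nothing.** It can be programmed as written, and the protocol prescribes no liver-injury algorithm. This stands: the point is about sensitivity, not an inconsistency.
- **Repeat testing may close the gap.** ALT, AST, ALP and total bilirubin belong to one chemistry panel (Protocol Table 12), and a repeat panel can itself meet the rule. This also stands in part. A reader might infer that repeats are drawn one analyte at a time and so defeat the rule, but Protocol 8.3.7 does not say that. Repeats can separate the elevations or capture them together. They make a missed pairing less likely without ruling it out, and the 21-day gap describes the schedule before any repeats.
- **The data are not lost.** Single values are listed and graded, and clinically meaningful abnormalities, or those requiring a change in study drug, are reported as adverse events (Protocol 9.1). This stands, so the consequence is a missing flag rather than missing data.
- **Any window length is a judgement.** True: the documents offer no basis for a particular length.

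None of this supplies a display that links the two elevations across visits.

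**Conclusion.** The point holds in a limited form. A participant who crosses the transaminase and bilirubin limits only at different visits is not flagged in Listing 2.8.8, the sole output that combines them. This rests on reading the same-visit condition literally and on finding no cross-visit rule elsewhere in either document.

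Two stronger readings are tempting and not supported. One is that every case with peaks at different visits is missed; pattern (b) shows otherwise. The other is that the plan will declare that no potential case occurred. SAP 8.3.3 plans a listing only, without a summary count or a concluding statement, so the risk lies in how a reader interprets an empty listing.

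The size cannot be given. The documents contain no rate of such elevations and no basis for one. About 164 participants are planned (82 + 82), so individual cases can be reviewed one by one. The effect is confined to one descriptive safety listing, and no efficacy endpoint is touched. This is an inexpensive improvement.

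**What to change.** In SAP 8.3.3, list any participant with a postbaseline ALT or AST of at least 3 × ULN and a total bilirubin of at least 2 × ULN within a prespecified number of days of each other, in either order, counting unscheduled draws. The window should span at least one cycle. Thirty days is an example and an assumption; it covers the 27-day longest gap under the visit windows. If a cycle start were postponed by the full 14 days in Protocol 6.5.1 with no draw in between, the gap would be 21 + 14 = 35 days, so the team should decide whether the window must cover that.

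For each listed participant, show all relevant dates and ALP values. Flag those with ALP below 2 × ULN, stating the time point at which ALP is judged, and those who meet the present same-visit rule, so that the present listing can still be recovered.

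The cost is a short text change and reprogramming of one listing, using data already collected. The downside is that some extra participants may be listed for review, including some with ALP of 2 × ULN or more whom the present rule leaves out.
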